 - PT control/reference level (assuming 12 seconds)
- Liver enzymes and function tests at hours 48, 96, 168
 - AST, ALT, total bilirubin, alkaline phosphatase, albumin
- MELD-Na Score at hours 48, 96, 168
 - INR, creatinine, bilirubin, sodium
- Documented tolerability at hours 24, 48, 96
 - Need for dose reduction, headache, dizziness, dry mouth, nausea, vomiting, flushing, rash, hypotension, treatment related adverse events
- Documented safety at hours 24, 48, 96
 - QTc Interval (EKG)
 - Crystalluria (Urinalysis with microscopy and pH testing)
- Serum Biomarkers
 - Procalcitonin, C-reactive protein, thrombomodulin, thromboelastography (TEG), Receptor for Advanced

Glycation End Products, Tissue Factor Pathway Inhibitor at study hours 0, 48, 96, 168 (When feasible)

- Ascorbate level at hour 0, 48, 96, 168 (When feasible)
- Need for escalation of support i.e. need for ventilator or pressor support when these are not needed at baseline
- ICU-free days at day 28
- All-cause mortality to day 28 and day 90
- Hospital-free days at day 90

Study Population: A total of 20 adult subjects with alcoholic hepatitis and suspected or documented sepsis will be enrolled in this study. All participants will be enrolled at the Virginia Commonwealth University Health System (VCUHS).

Phase: Phase II

[figure not shown]
Description of Sites/Facilities Enrolling Participants: Subjects will be recruited from the Emergency Department (ED), inpatient medicine unit admitted to the Digestive Health Service (DHS), and Intensive Care Units (ICU) at VCUHS.

[figure not shown]
Description of Study Intervention: Participants will be randomized to receive either intravenous Vitamin C (sterile L-ascorbic acid mixed in 5% dextrose in water) or placebo (5% dextrose in water). Active treatment will continue for 96 hours, discharge from study hospital, study withdrawal, or death, whichever comes first.

[figure not shown]
Study Duration: Years 1-4

[figure not shown]
Participant Duration: 90 days

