3 OBJECTIVES AND ENDPOINTS

| OBJECTIVES | ENDPOINTS | JUSTIFICATION FOR ENDPOINTS |
|---|--|---|
| Primary | | |
| Vitamin C infusion will significantly attenuate hepatic dysfunction as measured by the model for end stage liver disease (MELD) score | Change in MELD score at 96 hours as compared to baseline when compared to placebo. | MELD score is an independent positive predictor of mortality in patients with AH. |
| Secondary | | |

| OBJECTIVES | ENDPOINTS | JUSTIFICATION FOR ENDPOINTS |
|--|--|---|
| Vitamin C infusion will be safe and tolerable in patients with severe alcoholic hepatitis . | Documented side effects and serious adverse events at hours 24, 48, 96 when compared with hour zero in high dose ascorbic acid versus placebo. | AscA infusion may cause dry mouth, nausea, vomiting, dizziness, headache, flushing, rash, diarrhea. AscA can be excreted from kidney and lead to crystalluria, so will monitor urine pH via urinalysis. Will also monitor EKGs for QTc changes. |
| Secondary | | |
| Vitamin C infusion will attenuate biomarkers of inflammation (C-Reactive Protein, procalcitonin), vascular injury (Thrombomodulin, Angiopoietin-2), while inducing the onset of a fibrinolytic state (Tissue Factor Pathway Inhibitor) | Modulation of available biomarkers | Changes in these biomarkers may provide mechanistic insight into how vitamin C attenuates inflammation |
| Secondary | | |
| Vitamin C Infusion will improve clinical endpoints in this patient population . | 
Change in SOFA Score and Components at hours 48, 96, 168
 
Change in CLIF-SOFA scores and Components at hour 48, 96, 168 when compared to placebo
 
Change in MELD-Na, MDF, Lille scores at hour 48, 96, 168 when compared to placebo
 
Ascorbate level at hour 0, 48, 96, 168 (When feasible)
 
ICU-free days at day 28
 
All-cause mortality to day 28, 90
 
Hospital-free days at day 90
 | CLIF-SOFA, MDF, MELD, and Lille scores are associated with mortality in alcoholic hepatitis. Ascorbate levels are associated with mortality in sepsis patients in the ICU. AH patients have prolonged hospitalizations and are frequently in the ICU. |

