6.1.2 DOSING AND ADMINISTRATION

- 1) **First study drug dose** (L-ascorbic acid or placebo) will be considered “Dose 1” and will be administered within 6 hours of randomization or the earliest available time post any clinically indicated procedure which requires the patient to be off the unit. All doses will be administered in the medicine M9W inpatient unit or ICU. Patients receiving vitamin C will receive 25% of the total daily calculated dosing (200mg/kg/24 hours) and will be infused over 30 minutes for this first dosing.
- 2) **Subsequent doses** which represent 25% of the day’s total dose will be infused every six hours through 96 hours (+/- 3 hours).
 - a) Timing of Dose 2 will be triggered by the physician order for q 6 hour administration and will therefore be listed on the bedside MAR. As such, timing of Dose 2 may be out of the +/- 3 hour window and will not trigger a protocol deviation.
 - b) If for any reason any other maintenance dose is not administered within window, the dose will be skipped and the next scheduled dose will be given and documented in the data collection tool.

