9.4 STATISTICAL ANALYSES

9.4.1 GENERAL APPROACH

Continuous variables will be compared across groups using ANOVA or a Kruskal Wallis ANOVA depending on their distribution. Changes from baseline to time of measurement will be compared by analysis of covariance. Categorical variables will be measured by Fisher's Exact test. Correlations will be assessed by Spearman's coefficient.

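### ICU-free days at day 28 is compared without regard to whether the patient starts in the ICU; the test is valid overall, but a prespecified location-adjusted rank test would protect the single realised trial at almost no cost

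*Combined protocol and SAP*

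**What the plan says.** Section 1.1 lists "ICU-free days at day 28" and "Hospital-free days at day 90" among the secondary endpoints. On the population it says: "A total of 20 adult subjects with alcoholic hepatitis and suspected or documented sepsis will be enrolled in this study". On where they come from it says: "Subjects will be recruited from the Emergency Department (ED), inpatient medicine unit", and then adds the intensive care units; section 5.5 repeats the three sources. Section 3 supports the endpoint by noting that "AH patients have prolonged hospitalizations and are frequently in the ICU".

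Section 9.4.1 gives the test: "Continuous variables will be compared across groups using ANOVA or a Kruskal Wallis ANOVA depending on their distribution". Analysis of covariance is kept for changes from baseline, and a free-day count is not a change from baseline. Section 6.3 describes random batches of 2, 4 or 8 and uses the word stratified, but the only thing it names is the two study arms. Section 9.2 sets 10 patients per arm.

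On location, section 6.1.2 says: "All doses will be administered in the medicine M9W inpatient unit or ICU". The schedule of activities (section 1.3) has a row for ICU-free days at day 28 but none for unit of care at hour 0.

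**The concern.** Starting location is partly built into this endpoint. A patient already in the ICU at hour 0 is losing ICU-free days from the outset, whereas a ward patient who is never transferred loses none unless death is counted. With 10 per arm and nothing in the randomisation to balance location, one arm can easily receive more ICU starters. The planned test has no means of allowing for that.

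Two things are at stake: whether the one observed difference in ICU-free days can be read as a treatment effect when the arms are visibly unbalanced, and whether the comparison is as sensitive as the data allow. If the adjustment is chosen only after an imbalance is seen, it will be post hoc and hard to defend.

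**Working it through.** **The plan's own figure.** The documents give no planning figure for ICU-free days. The only sample size is for MELD: a 25% fall from 29 is 7.25 points with SD 5, so n = 2 × (1.96 + 0.84)² × 5² / 7.25² = 7.5, rounded up to 8 per arm, as section 9.2 states. It is then raised to 10. Only the 10 per arm is used below.

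**Step 1: chance of imbalance.** Let K of the 20 patients start in the ICU and let location be unrelated to order of entry. The number of ICU starters in one arm is then hypergeometric.

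- K = 10, split 7:3 or worse: 2 × [C(10,7)² + C(10,8)² + C(10,9)² + C(10,10)²] / C(20,10) = 2 × (14,400 + 2,025 + 100 + 1) / 184,756 = 17.9%.
- K = 8 (or 12), difference of 4 or more: 2 × (13,860 + 1,760 + 66) / 184,756 = 17.0%.
- K = 6 (or 14), difference of 4 or more: 2 × (12,012 + 1,001) / 184,756 = 14.1%.

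For odd K the difference can only be odd. Over K = 7, 9, 11 and 13, a difference of 3 or more has probability 35% to 37%, and 5 or more has 6% to 7%.

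**Step 2: effect on the arm difference.** If ICU and non-ICU starters differ by G days on average, an excess of d ICU starters in one arm shifts the difference in means by (d / 10) × G with no drug effect. At 7:3, d = 4 and the shift is 0.4G: 2.0 days for G = 5, 3.2 for G = 8 and 4.0 for G = 10. The values of G are assumptions.

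**Step 3: simulated error rate and power.** All inputs are assumed:

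- 10 of 20 start in the ICU.
- Deaths score 0. The plan states no rule.
- 28-day mortality is 45% for ICU starters and 20% for others.
- ICU stay is log-normal, median 6 days, log-SD 0.8.
- 20% of non-ICU starters are transferred to the ICU.

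Mean ICU-free days are then 10.8 and 21.0, a gap of 10.2 days, at the top of the range in step 2. There were 60,000 trials per setting. Rank ANCOVA is a regression of the ranks on arm and ICU location.

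| Setting | Kruskal-Wallis | Rank ANCOVA |
|---|---|---|
| No effect, all trials | 4.9% | 5.1% |
| No effect, split 5:5 | 2.0% | 5.3% |
| No effect, split 7:3 | 11.1% | 4.8% |
| Very strong effect (odds of death and transfer × 0.22, stay halved) | 22% | 36% |
| Same effect, 7 of the 10 ICU starters on vitamin C | 2% | 24% |
| Same effect, 7 of the 10 ICU starters on placebo | 70% | 38% |
| Moderate effect (odds × 0.5, stay × 0.8) | 9% | 11% |
| Moderate effect, 4 of 20 in ICU | 9% | 10% |

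With a weaker influence of location (mortality 40% v 30%, median stay 4 days, 40% transferred), the gap is 17.9 − 13.3 = 4.6 days. The null rejection rate at 7:3 is 7.3% v 5.2%, and power for the moderate effect is 12% v 14%. Other runs under the main assumptions gave 21% to 23% v 34% to 37% for the very strong effect and up to 12% adjusted for the moderate one.

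**Step 4: hospital-free days.** All patients are in hospital at hour 0, so location is not built into this count. Three assumed settings were simulated for ICU v non-ICU starters:

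- mortality 25% v 15%, mean stay 20 v 14 days;
- mortality 45% v 30%, mean stay 24 v 16 days;
- mortality 60% v 45%, mean stay 26 v 18 days.

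The effect was risk of death × 0.3 and stay × 0.6. Power of the unadjusted and location-stratified rank tests was 34% v 33%, 42% v 41% and 53% v 51%. Given a 7:3 or worse split, the null rejection rate was about 7% v 5%.

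**The case against.** The strongest reply is that randomisation already makes the planned comparison valid. Averaged over all allocations it rejects a true null about 5% of the time, so covariate adjustment is a gain in efficiency and not the repair of an error. That stands. A reader might infer from the 11% at a 7:3 split that the planned test has an inflated error rate; it does not. The excess in unbalanced trials is offset by rejection well below 5% in balanced ones. What remains is that the sponsor will interpret one allocation, and about one in six may be this unbalanced.

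A reader might also infer that much power is lost. The documents do not support that. They give no ICU share, ICU stay, transfer rate, mortality by location, or mean and SD for the endpoint. The large gains need a very strong drug effect; for a moderate one both tests have power near 10%.

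A third tempting extension is to hospital-free days. Step 4 shows no power gain there and only a small conditional distortion.

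Finally, section 6.1.2 says where doses are given, not where the patient is at hour 0, and Dose 1 may follow randomisation by 6 hours or longer. A patient waiting in the ED for an ICU bed could be misclassified. This is a fair criticism of a bare ICU versus non-ICU label, and the fix must deal with it.

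**Conclusion.** The point holds for ICU-free days at day 28. No adjustment or stratification for starting location is planned, although the trial mixes ED, ward and ICU starters. Overall type I error is about 5%. For even ICU totals from 6 to 14, a difference of 4 or more ICU starters between arms arises by chance in 14% to 18% of trials. At 7:3 it moves the arm difference by 0.4 times the location gap, 2 to 4 days for an assumed gap of 5 to 10 days. It can mimic or mask an effect in that trial. Power gains run from 2 or 3 points to about 13 to 15 points, depending on an effect size, ICU share, mortality and stay that are all assumed.

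This concerns one secondary endpoint of a 20-patient proof-of-concept trial. The primary MELD analysis is unaffected. The change is worth making because it costs little and is credible only if made in advance.

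**What to change.** In section 9.4.1, state before unblinding that ICU-free days at day 28 will be compared by rank ANCOVA, or by a van Elteren test, with ICU versus non-ICU location at hour 0 as covariate or stratum. Name one of the two. Rank ANCOVA is the easier choice if ICU starters are few, because a stratum with patients in only one arm contributes nothing to the van Elteren test.

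Define location from the admission and transfer dates that the endpoint already needs, and give a rule for patients still in the ED, for example the unit assigned at randomisation. State how deaths are scored in the count, since either analysis depends on it. Keep the unadjusted Kruskal-Wallis as a supporting result. Hospital-free days at day 90 may use the same model for consistency, without claiming a gain.

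The cost is a few lines of text, one degree of freedom and one recorded field. No extra visit or test is needed.

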1.2 SCHEMA

1.3 SCHEDULE OF ACTIVITIES (SOA)

| Assessments | Hour 0 | Q 24 hrs 1st 7 days or in ICU | Hour 48 | Hour 96 | Hour 168 | Day 28 | Day 90 |
|---|--------------------------|--|---------------------------|---------------------------|----------------------------|--------------------------|--------------------------|
| VS: BP, HR, MAP, RR, Temp., O2 sats, CVP, Glasgow Coma Scale, West-Haven Scale | S | | S | S | S | | |
| Body Weight | S | | S | S | | | |
| Suspected or known site of sepsis | S | | S | S | S | R | R |
| I/Os Total and Urine and urinalysis for crystalluria | S | R | R | R | | | |
| Assessment of Renal Function with serum creatinine, urine output and Use of Dialysis | S | | S | S | S | S | |
| Calculate MELD Score (most study by biostatistician) | S | | S | S | S | | |
| Labs: Arterial Blood Gases, Na+, K+, BUN, Cr, WBC, Hgb, Hct, Platelets, PT/INR | S | | S | S | S | | |
| Bilirubin Total, AST, ALT, ALP, albumin | S | | S | S | S | | |
| Need for Vasopressors or Inotropes: Epi, Nor-epi, Phenylephrine, Vasopressin, Dopamine | S | | S | S | S | | |
| All concomitant medications including: Methylprednisone, Hydrocortisone, N-acetylcysteine, Antibiotics, Thiamine, Albumin | S | | S | S | S | | |
| AE/SAE Assessments | R | | R | R | R | | |
| Blood for Biomarkers and TEG | R | | R | R | R | | |
| ICU Free Days | | | | | | R | |
| Hospital Free Days | | | | | | | R |
| Glucose Monitoring | S | S | S | S | S | | |
| EKG Monitoring | S | R | R | R | | | |
| All-Cause Mortality | | | | | | R | R |

S = Standard of Care
R = Research

2 INTRODUCTION

[figure not shown]
2.1 STUDY RATIONALE

Alcoholic hepatitis is a clinical syndrome characterized by development of rapid onset of jaundice and systemic inflammation in the setting of heavy alcohol (1). Recent guidelines have proposed a standardized definition of AH consisting of the clinical development of hepatitis in the setting of heavy alcohol use, along with a serum bilirubin >3 mg/dL, aspartate aminotransferase (AST) >50 IU/ml and <500 IU/ml, an AST: alanine aminotransferase (ALT) ratio of >1.5, and exclusion of other causes of acute hepatitis such as viral, autoimmune, or metabolic etiologies (2). The diagnosis of AH is associated with high rates of mortality (3). Various scoring systems such as the Maddrey Discriminate Function (MDF) Model for End Stage Liver Disease (MELD), and Lille Model have been developed to predict mortality in alcoholic hepatitis patients (4,5).

Recent data indicated the mortality due to alcoholic cirrhosis is increasing, in particular younger people age 25-34 (6). The main driver of morbidity and mortality in AH patients are infections (7). However, clinical trials of AH exclude patients with suspected or documented infection (8). There are currently no FDA approved therapies for AH. Current guidelines by the American Association for the Study of Liver Disease (AASLD) recommend corticosteroids for the treatment of severe AH (9). However, corticosteroids only have a short-term mortality benefit at 28 days and are associated with higher risks of infection, so therefore contraindicated in patients with AH and suspected or documented sepsis (10).

In this study, we will test the novel hypothesis that high-dose ascorbic acid (AscA or Vitamin C) will improve outcomes of AH patients with sepsis.

2.2 BACKGROUND

[figure not shown]

AH is associated with numerous pathophysiological mechanisms that increase predisposition to sepsis (Figure 1) (11). High levels of alcohol consumption impair the gut epithelial barrier and increase bacterial translocation and endotoxemia (12). In animal models, alcohol ingestion also increases markers of oxidative stress (13). Activated Kupffer cells and hepatocytes are the likely source of free radicals (14,15). Oxidative stress mediates alcohol induced liver injury via cytochrome P-450 system and leads to mitochondrial damage, activation of apoptosis, and up regulation of lipid synthesis (16, 17,18,19). There is also a release of damage and pathogen associated molecular pattern (DAMP and

PAMP) signals that enhance activation of the innate immune system (20) These signals set up a systemic inflammatory state which is further amplified by the systemic response to infection (21) At the same time, there are changes in neutrophil, lymphocyte and macrophage function that impair the ability to clear infection while enhancing oxidative stress and tissue injury (22 23).

Use of High Dose Ascorbic Acid in Patients with AH and Sepsis

Vitamin C or Ascorbic acid (AscA) has been shown to have pleiotropic effects in sepsis such as reducing oxidative stress, improving neutrophil function and bacterial clearance, reducing systemic inflammatory cytokines, and improving endogenous catecholamine synthesis (Figure 2) (24, 25, 26, 27). AscA cannot be synthesized in humans and serum levels are dependent on diet (28). Serum levels of AscA are reduced in patients with sepsis and lower levels correlate with higher mortality (29). AscA levels in serum and liver tissue have been shown to be reduced in patients with alcoholic liver disease (30). In critically ill patients, intravenous administration of AscA is necessary to maintain supra-physiological levels (31, 32). In a phase 1 randomized clinical trial of patients with severe sepsis, high dose intravenous AscA was safe with no adverse events and demonstrated a reduction in inflammatory markers and organ dysfunction compared with placebo (33). Previous clinical trials in AH have only administered anti-oxidants via the oral route and excluded patients with infection (34). Therefore, the purpose of this clinical trial is to examine the safety, tolerability, and efficacy of high dose intravenous AscA in patients with severe AH and sepsis.

Preliminary Data To Support the Use of AscA in AH and Sepsis

AscA prevents pulmonary neutrophil infiltration in a feces-induced peritonitis (FIP) model of sepsis (Figure 3).

[figure not shown]

Figure 3a: AscA (200 mg/kg) infused 30 min following onset of feces Induced peritonitis (FIP) attenuates sepsis-mediated acute lung injury in wild type mice at 16 hours. (H&E stain, 40X magnification)

Figure 3b: AscA (200 mg/kg) infused 30 min after feces induced peritonitis significantly attenuated neutrophil sequestration in murine lung at 16 hours. (Anti-murine PMN monoclonal antibody, 40X Mag)

AsCA Increased Clearance of Bacteria from Circulation in a Preclinical Model of Sepsis

[figure not shown]

Figure 4: Blood cultures from septic mice after FIP onset. AscA treated mice (200 mg/kg) show significantly lower colony forming units per 10 µl of blood compared to untreated septic animals.

In the same murine model of sepsis, blood was obtained by cardiac puncture at the time of euthanasia using sterile technique varying time points after induction of feces induced peritonitis with or without associated AscA administration (Figure 4). 10 µl of blood was plated on agar plates and colonies counted after overnight incubation. AscA treated mice had a highly significant decrease in colony counts compared to untreated mice ($p < 0.01$). Bronchoalveolar lavage in these mice also demonstrated an increased in alveolar protein content after induction of FIP and protection from AscA (data not shown).

Human Data to Support the Safety and Efficacy of AscA in Humans with Sepsis

[figure not shown]

Figure 5: Patients with severe sepsis have low plasma ascorbate levels. Intermittent intravenous vitamin C infusion produces rapid, sustained increases in plasma ascorbate levels.

A phase I, randomized, double blind, placebo-controlled trial, testing the safety of parenteral vitamin C in patients with severe sepsis was initiated at the VCU Medical Center. All patients enrolled, regardless of study arm, received full ICU standard of care. Patients were randomized to placebo (5% dextrose/water, D5W), or low dose vitamin C (50 mg/kg/24hr), or high dose vitamin C (200 mg/kg/24hr). The calculated 24 hour dosage was divided into four and administered intravenously (in 50 ml D5W) over 30 minutes every 6 hours for 96 hours. Vital signs were monitored every 5 minutes during infusion and for 45 minutes afterwards by bedside ICU Nursing and the investigative team. Plasma AscA was measured by HPLC at varying

time points after entry (Figure 5). At entry, the levels were sub-normal in all cases.

[figure not shown]

Figure 6: High dose vitamin C significantly reduces sequential organ failure assessment (SOFA) scores during the 96 hour treatment period when compared to placebo.

While they did not change in the placebo arm, both high-dose and low dose AscA achieved steady state within 24 hours. AscA improved SOFA scores (Fig 6). The SOFA scores were plotted over time of entry. While the placebo arm remained relatively flat with a small trend upwards, both low and high dose AscA decreased the SOFA scores over the 96 hours of infusion.

AscA produced a trend towards decreased mortality (Figure 7): In this pilot study which was not powered to evaluate mortality, there was a trend for decreased mortality at day 28. These data formed the basis for an ongoing phase 2B trial of AscA for severe sepsis funded by the NHLBI and led by the [name] (co-PI).

[figure not shown]

Figure 7: Vitamin C infusion reduces 28-day mortality in patients with severe sepsis

AscA decreased hsCRP and procalcitonin: In the placebo arm, the CRP (left panel) and procalcitonin (right panel) remained flat and then either decreased (CRP) or showed an increase (procalcitonin). In contrast, both doses of AscA reduced both hsCRP and procalcitonin (Figure 8).

[figure not shown]

Figure 8: Intravenous vitamin C rapidly lowers inflammatory biomarkers (CRP, PCT) in patients with severe sepsis

